14. TABLE AND LISTING SHELLS

Table 14.1.1
Participant Disposition
All Participants

	Cohort A EC CPI-Nai (N = XX) n (%)	Head and Neck (N = XX) n (%)	Cohort C Cervical (N = XX) n (%)	Cohort E TMB-H/MSS (N = XX) n (%)	Cohort F Rare Tumors (N = XX) n (%)	Cohort G Post-CPI (N = XX) n (%)	Cohort H Ovarian (N = XX) n (%)	Total (N = XX) n (%)
Screened	X	X	X	X	X	X	X	X
Screen Failure	X	X	X	X	X	X	X	X
Intention-to-Treat Analysis Set [1]	X	X	X	X	X	X	X	X
Safety Analysis Set [2]	X (XX.X)	X (XX.X)	X (XX.X)	X (XX.X)	X (XX.X)	X (XX.X)	X (XX.X)	X (XX.X)
Response-Evaluable Analysis Set [3]	X (XX.X)	X (XX.X)	X (XX.X)	X (XX.X)	X (XX.X)	X (XX.X)	X (XX.X)	X (XX.X)
Received at Least One Dose of								
Etigilimab	X (XX.X)	X (XX.X)	X (XX.X)	X (XX.X)	X (XX.X)	X (XX.X)	X (XX.X)	X (XX.X)
Nivolumab	X (XX.X)	X (XX.X)	X (XX.X)	X (XX.X)	X (XX.X)	X (XX.X)	X (XX.X)	X (XX.X)
Completed all Dosing Cycles	X (XX.X)	X (XX.X)	X (XX.X)	X (XX.X)	X (XX.X)	X (XX.X)	X (XX.X)	X (XX.X)
Completed Treatment Termination Visit	X (XX.X)	X (XX.X)	X (XX.X)	X (XX.X)	X (XX.X)	X (XX.X)	X (XX.X)	X (XX.X)
Completed Follow-up Visit	X (XX.X)	X (XX.X)	X (XX.X)	X (XX.X)	X (XX.X)	X (XX.X)	X (XX.X)	X (XX.X)
Discontinued Treatment	X (XX.X)	X (XX.X)	X (XX.X)	X (XX.X)	X (XX.X)	X (XX.X)	X (XX.X)	X (XX.X)
Reason for Discontinuation								
XXXXX	X (XX.X)	X (XX.X)	X (XX.X)	X (XX.X)	X (XX.X)	X (XX.X)	X (XX.X)	X (XX.X)
XXXXX	X (XX.X)	X (XX.X)	X (XX.X)	X (XX.X)	X (XX.X)	X (XX.X)	X (XX.X)	X (XX.X)
XXXXX	X (XX.X)	X (XX.X)	X (XX.X)	X (XX.X)	X (XX.X)	X (XX.X)	X (XX.X)	X (XX.X)
XXXXX	X (XX.X)	X (XX.X)	X (XX.X)	X (XX.X)	X (XX.X)	X (XX.X)	X (XX.X)	X (XX.X)
Discontinued Study	X (XX.X)	X (XX.X)	X (XX.X)	X (XX.X)	X (XX.X)	X (XX.X)	X (XX.X)	X (XX.X)
Reason for Discontinuation								
XXXXX	X (XX.X)	X (XX.X)	X (XX.X)	X (XX.X)	X (XX.X)	X (XX.X)	X (XX.X)	X (XX.X)
XXXXX	X (XX.X)	X (XX.X)	X (XX.X)	X (XX.X)	X (XX.X)	X (XX.X)	X (XX.X)	X (XX.X)
XXXXX	X (XX.X)	X (XX.X)	X (XX.X)	X (XX.X)	X (XX.X)	X (XX.X)	X (XX.X)	X (XX.X)
XXXXX	X (XX.X)	X (XX.X)	X (XX.X)	X (XX.X)	X (XX.X)	X (XX.X)	X (XX.X)	X (XX.X)

[1] Intention-to-Treat Analysis Set: All subjects who signed an informed consent form and were enrolled into the study.

[2] Safety Analysis Set: All subjects who received any amount of study drug.

[3] Response Evaluable Analysis Set: All subjects with measurable disease at baseline, with at least one post-baseline response assessment or discontinues treatment due to disease progression or death within 16 weeks of first dose of study drug.

Note: No subjects were recruited into Cohort D and so this cohort is not displayed.

Note: The Intention-to-Treat Analysis Set is used as the denominator for all percentages.

Source: Listing 16.2.1.1 and 16.2.3

Table 14.1.2.1
Demography
Safety Analysis Set

		Cohort A EC CPI-Naive (N = XX)	Cohort B Head and Neck (N = XX)	Cohort C Cervical (N = XX)	Cohort E TMB-H/MSS (N = XX)	Cohort F Rare Tumors (N = XX)	Cohort G Post-CPI (N = XX)	Cohort H Ovarian (N = XX)	Total (N = XX)
Age	n	X	X	X	X	X	X	X	X
	Mean (SD)	XX.X (XX.XX)	XX.X (XX.XX)	XX.X (XX.XX)	XX.X (XX.XX)	XX.X (XX.XX)	XX.X (XX.XX)	XX.X (XX.XX)	XX.X (XX.XX)
	Median	XX.X	XX.X	XX.X	XX.X	XX.X	XX.X	XX.X	XX.X
	Q1, Q3	XX.X, XX.X	XX.X, XX.X	XX.X, XX.X	XX.X, XX.X	XX.X, XX.X	XX.X, XX.X	XX.X, XX.X	XX.X, XX.X
	Min, Max	XX, XX	XX, XX	XX, XX	XX, XX	XX, XX	XX, XX	XX, XX	XX, XX
Sex									
Male	n (%)	XX (XX.X)	XX (XX.X)	XX (XX.X)	XX (XX.X)	XX (XX.X)	XX (XX.X)	XX (XX.X)	XX (XX.X)
Female	n (%)	XX (XX.X)	XX (XX.X)	XX (XX.X)	XX (XX.X)	XX (XX.X)	XX (XX.X)	XX (XX.X)	XX (XX.X)
Race									
American Indian or Alaska Native	n (%)	XX (XX.X)	XX (XX.X)	XX (XX.X)	XX (XX.X)	XX (XX.X)	XX (XX.X)	XX (XX.X)	XX (XX.X)
Asian	n (%)	XX (XX.X)	XX (XX.X)	XX (XX.X)	XX (XX.X)	XX (XX.X)	XX (XX.X)	XX (XX.X)	XX (XX.X)
Black or African American	n (%)	XX (XX.X)	XX (XX.X)	XX (XX.X)	XX (XX.X)	XX (XX.X)	XX (XX.X)	XX (XX.X)	XX (XX.X)
Native Hawaiian or Other									
Pacific Islander	n (%)	XX (XX.X)	XX (XX.X)	XX (XX.X)	XX (XX.X)	XX (XX.X)	XX (XX.X)	XX (XX.X)	XX (XX.X)
White	n (%)	XX (XX.X)	XX (XX.X)	XX (XX.X)	XX (XX.X)	XX (XX.X)	XX (XX.X)	XX (XX.X)	XX (XX.X)
Other	n (%)	XX (XX.X)	XX (XX.X)	XX (XX.X)	XX (XX.X)	XX (XX.X)	XX (XX.X)	XX (XX.X)	XX (XX.X)
Ethnicity									
Hispanic or Latino	n (%)	XX (XX.X)	XX (XX.X)	XX (XX.X)	XX (XX.X)	XX (XX.X)	XX (XX.X)	XX (XX.X)	XX (XX.X)
Not Hispanic or Latino	n (%)	XX (XX.X)	XX (XX.X)	XX (XX.X)	XX (XX.X)	XX (XX.X)	XX (XX.X)	XX (XX.X)	XX (XX.X)
Child-Bearing Potential									
Yes	n (%)	XX (XX.X)	XX (XX.X)	XX (XX.X)	XX (XX.X)	XX (XX.X)	XX (XX.X)	XX (XX.X)	XX (XX.X)
No	n (%)	XX (XX.X)	XX (XX.X)	XX (XX.X)	XX (XX.X)	XX (XX.X)	XX (XX.X)	XX (XX.X)	XX (XX.X)

Note: No subjects were recruited into Cohort D and so this cohort is not displayed.

Note: Percentages are based on the safety analysis set.

Source: Listing 16.2.4.1

Programming Note: Repeat the table for the sub-cohorts in Cohort F using this shell.

Table 14.1.3.1
Baseline Disease Characteristics
Safety Analysis Set

	Cohort A EC CPI-Naive (N = XX)	Cohort B Head and Neck (N = XX)	Cohort C Cervical (N = XX)	Cohort E TMB-H/MSS (N = XX)	Cohort F Rare Tumors (N = XX)	Cohort G Post-CPI (N = XX)	Cohort H Ovarian (N = XX)	Total (N = XX)
Time Since Initial Diagnosis	n Mean (SD) Median Q1, Q3 Min, Max	X XX.X (XX.XX) XX.X XX.X, XX.X XX, XX						
Primary Tumor Location	n (%)	XX (XX.X)						
Head and Neck	n (%)	XX (XX.X)						
Gastric	n (%)	XX (XX.X)						
Cervical	n (%)	XX (XX.X)						
Endometrial	n (%)	XX (XX.X)						
Germ Cell	n (%)	XX (XX.X)						
Sarcoma	n (%)	XX (XX.X)						
Salivary Gland	n (%)	XX (XX.X)						
Mesothelioma	n (%)	XX (XX.X)						
Uveal Melanoma	n (%)	XX (XX.X)						
Ovarian	n (%)	XX (XX.X)						
Other	n (%)	XX (XX.X)						
Tumor Staging at Initial Diagnosis	n (%)	XX (XX.X)						
1A	n (%)	XX (XX.X)						
1B	n (%)	XX (XX.X)						
1C	n (%)	XX (XX.X)						
2A	n (%)	XX (XX.X)						
2B	n (%)	XX (XX.X)						
2C	n (%)	XX (XX.X)						
3A	n (%)	XX (XX.X)						
3B	n (%)	XX (XX.X)						
3C	n (%)	XX (XX.X)						
4A	n (%)	XX (XX.X)						
4B	n (%)	XX (XX.X)						
4C	n (%)	XX (XX.X)						
Unknown/Other	n (%)	XX (XX.X)						
Tumor TMB High	n (%)	XX (XX.X)						
Yes	n (%)	XX (XX.X)						
No	n (%)	XX (XX.X)						
Tumor MSS	n (%)	XX (XX.X)						
Yes	n (%)	XX (XX.X)						
No	n (%)	XX (XX.X)						
Locally Advanced								

Yes	n (%)	XX (XX.X)							
No	n (%)	XX (XX.X)							
Metastatic									
Yes	n (%)	XX (XX.X)							
No	n (%)	XX (XX.X)							
PD-L1 TPS									
< 1%	n (%)	XX (XX.X)							
1 - 49%	n (%)	XX (XX.X)							
>= 50%	n (%)	XX (XX.X)							
Not Done	n (%)	XX (XX.X)							
Other	n (%)	XX (XX.X)							
PD-L1 CPS									
< 1%	n (%)	XX (XX.X)							
1 - 10%	n (%)	XX (XX.X)							
> 10%	n (%)	XX (XX.X)							
Not Done	n (%)	XX (XX.X)							
Other	n (%)	XX (XX.X)							

Note: No subjects were recruited into Cohort D and so this cohort is not displayed.

Note: Percentages are based on the safety analysis set.

Source: Listing 16.2.4.2 and 16.2.4.3

Programming Note: Repeat the table for the sub-cohorts in Cohort F using this shell.

Table 14.1.4.1
Prior Cancer Treatments
Safety Analysis Set

		Cohort A EC CPI-Naive (N = XX)	Cohort B Head and Neck (N = XX)	Cohort C Cervical (N = XX)	Cohort E TMB-H/MSS (N = XX)	Cohort F Rare Tumors (N = XX)	Cohort G Post-CPI (N = XX)	Cohort H Ovarian (N = XX)	Total (N = XX)
Number of Lines of Therapy									
0	n (%)	XX (XX.X)	XX (XX.X)	XX (XX.X)	XX (XX.X)	XX (XX.X)	XX (XX.X)	XX (XX.X)	XX (XX.X)
1	n (%)	XX (XX.X)	XX (XX.X)	XX (XX.X)	XX (XX.X)	XX (XX.X)	XX (XX.X)	XX (XX.X)	XX (XX.X)
2	n (%)	XX (XX.X)	XX (XX.X)	XX (XX.X)	XX (XX.X)	XX (XX.X)	XX (XX.X)	XX (XX.X)	XX (XX.X)
3	n (%)	XX (XX.X)	XX (XX.X)	XX (XX.X)	XX (XX.X)	XX (XX.X)	XX (XX.X)	XX (XX.X)	XX (XX.X)
>=4	n (%)	XX (XX.X)	XX (XX.X)	XX (XX.X)	XX (XX.X)	XX (XX.X)	XX (XX.X)	XX (XX.X)	XX (XX.X)
Biologic or Immunotherapy									
Yes	n (%)	XX (XX.X)	XX (XX.X)	XX (XX.X)	XX (XX.X)	XX (XX.X)	XX (XX.X)	XX (XX.X)	XX (XX.X)
No	n (%)	XX (XX.X)	XX (XX.X)	XX (XX.X)	XX (XX.X)	XX (XX.X)	XX (XX.X)	XX (XX.X)	XX (XX.X)
Chemotherapy									
Yes	n (%)	XX (XX.X)	XX (XX.X)	XX (XX.X)	XX (XX.X)	XX (XX.X)	XX (XX.X)	XX (XX.X)	XX (XX.X)
No	n (%)	XX (XX.X)	XX (XX.X)	XX (XX.X)	XX (XX.X)	XX (XX.X)	XX (XX.X)	XX (XX.X)	XX (XX.X)
Surgery									
Yes	n (%)	XX (XX.X)	XX (XX.X)	XX (XX.X)	XX (XX.X)	XX (XX.X)	XX (XX.X)	XX (XX.X)	XX (XX.X)
No	n (%)	XX (XX.X)	XX (XX.X)	XX (XX.X)	XX (XX.X)	XX (XX.X)	XX (XX.X)	XX (XX.X)	XX (XX.X)
Radiotherapy									
Yes	n (%)	XX (XX.X)	XX (XX.X)	XX (XX.X)	XX (XX.X)	XX (XX.X)	XX (XX.X)	XX (XX.X)	XX (XX.X)
No	n (%)	XX (XX.X)	XX (XX.X)	XX (XX.X)	XX (XX.X)	XX (XX.X)	XX (XX.X)	XX (XX.X)	XX (XX.X)

Note: No subjects were recruited into Cohort D and so this cohort is not displayed.

Note: Percentages are based on the safety analysis set.

Source: Listing 16.2.4.4.2, 16.2.4.4.3, 16.2.4.4.4, 16.2.4.4.5

Table 14.1.4.2
Other Prior Medications
Safety Analysis Set

Drug Class (L2)/ WHO Drug Preferred Base Name [1]	Cohort A		Cohort B		Cohort C		Cohort E		Cohort F		Cohort G		Cohort H		Total (N = XX)
	EC CPI-Naïve (N = XX)	n (%)	Head and Neck (N = XX)	n (%)	Cervical (N = XX)	n (%)	TMB-H/MSS (N = XX)	n (%)	Rare Tumors (N = XX)	n (%)	Post-CPI (N = XX)	n (%)	Ovarian (N = XX)	n (%)	
Number of Participants with any Medication	XX (XX.X)		XX (XX.X)		XX (XX.X)		XX (XX.X)		XX (XX.X)		XX (XX.X)		XX (XX.X)		XX (XX.X)
Drug Class 1	XX (XX.X)		XX (XX.X)		XX (XX.X)		XX (XX.X)		XX (XX.X)		XX (XX.X)		XX (XX.X)		XX (XX.X)
WHO Drug Name 1	XX (XX.X)		XX (XX.X)		XX (XX.X)		XX (XX.X)		XX (XX.X)		XX (XX.X)		XX (XX.X)		XX (XX.X)
WHO Drug Name 2	XX (XX.X)		XX (XX.X)		XX (XX.X)		XX (XX.X)		XX (XX.X)		XX (XX.X)		XX (XX.X)		XX (XX.X)
Drug Class 2	XX (XX.X)		XX (XX.X)		XX (XX.X)		XX (XX.X)		XX (XX.X)		XX (XX.X)		XX (XX.X)		XX (XX.X)
WHO Drug Name 1	XX (XX.X)		XX (XX.X)		XX (XX.X)		XX (XX.X)		XX (XX.X)		XX (XX.X)		XX (XX.X)		XX (XX.X)
WHO Drug Name 2	XX (XX.X)		XX (XX.X)		XX (XX.X)		XX (XX.X)		XX (XX.X)		XX (XX.X)		XX (XX.X)		XX (XX.X)

[1] WHO Drug Dictionary Global version 2023(March 2023). L2: The second level of Anatomical Therapeutic Chemical (ATC) classification.
Note: No subjects were recruited into Cohort D and so this cohort is not displayed.

Note: Percentages are based on the safety analysis set.

Source: Listing 16.2.4.4.6

Table 14.1.4.3
Concomitant Medications
Safety Analysis Set

Drug Class (L2)/ WHO Drug Preferred Base Name [1]	Cohort B		Cohort C Cervical (N = XX) n (%)	Cohort E TMB-H/MSS (N = XX) n (%)	Cohort F Rare Tumors (N = XX) n (%)	Cohort G Post-CPI (N = XX) n (%)	Cohort H Ovarian (N = XX) n (%)	Total (N = XX) n (%)
	Cohort A EC CPI-Naïve (N = XX) n (%)	Head and Neck (N = XX) n (%)						
Number of Participants with any Medication	XX (XX.X)	XX (XX.X)	XX (XX.X)	XX (XX.X)	XX (XX.X)	XX (XX.X)	XX (XX.X)	XX (XX.X)
Drug Class 1	XX (XX.X)	XX (XX.X)	XX (XX.X)	XX (XX.X)	XX (XX.X)	XX (XX.X)	XX (XX.X)	XX (XX.X)
WHO Drug Name 1	XX (XX.X)	XX (XX.X)	XX (XX.X)	XX (XX.X)	XX (XX.X)	XX (XX.X)	XX (XX.X)	XX (XX.X)
WHO Drug Name 2	XX (XX.X)	XX (XX.X)	XX (XX.X)	XX (XX.X)	XX (XX.X)	XX (XX.X)	XX (XX.X)	XX (XX.X)
Drug Class 2	XX (XX.X)	XX (XX.X)	XX (XX.X)	XX (XX.X)	XX (XX.X)	XX (XX.X)	XX (XX.X)	XX (XX.X)
WHO Drug Name 1	XX (XX.X)	XX (XX.X)	XX (XX.X)	XX (XX.X)	XX (XX.X)	XX (XX.X)	XX (XX.X)	XX (XX.X)
WHO Drug Name 2	XX (XX.X)	XX (XX.X)	XX (XX.X)	XX (XX.X)	XX (XX.X)	XX (XX.X)	XX (XX.X)	XX (XX.X)

[1] WHO Drug Dictionary Global version 2023(March 2023). L2: The second level of Anatomical Therapeutic Chemical (ATC) classification.

Note: No subjects were recruited into Cohort D and so this cohort is not displayed.

Note: Percentages are based on the safety analysis set.

Source: Listing 16.2.4.4.6

Table 14.1.5
Investigational Product Exposure
Safety Analysis Set

	Cohort A		Cohort B		Cohort C		Cohort E		Cohort F		Cohort G		Cohort H		Total
	EC	CPI-Naïve (N = XX)	Head and Neck (N = XX)	Cervical (N = XX)	TMB-H/MSS (N = XX)	Rare Tumors (N = XX)	Post-CPI (N = XX)	Ovarian (N = XX)							
Etigilimab															
Number of Doses Received	n	X	X	X	X	X	X	X	X	X	X	X	X	X	X
Mean (SD)		XX.X (XX.XX)	XX.X (XX.XX)	XX.X (XX.XX)	XX.X (XX.XX)	XX.X (XX.XX)	XX.X (XX.XX)	XX.X (XX.XX)	XX.X (XX.XX)	XX.X (XX.XX)	XX.X (XX.XX)	XX.X (XX.XX)	XX.X (XX.XX)	XX.X (XX.XX)	XX.X (XX.XX)
Median		XX.X	XX.X	XX.X	XX.X	XX.X	XX.X	XX.X	XX.X	XX.X	XX.X	XX.X	XX.X	XX.X	XX.X
Q1, Q3		XX.X, XX.X	XX.X, XX.X	XX.X, XX.X	XX.X, XX.X	XX.X, XX.X	XX.X, XX.X	XX.X, XX.X	XX.X, XX.X	XX.X, XX.X	XX.X, XX.X	XX.X, XX.X	XX.X, XX.X	XX.X, XX.X	XX.X, XX.X
Min, Max		XX, XX	XX, XX	XX, XX	XX, XX	XX, XX	XX, XX	XX, XX	XX, XX	XX, XX	XX, XX	XX, XX	XX, XX	XX, XX	XX, XX
Total Dose Received (mg)	n	X	X	X	X	X	X	X	X	X	X	X	X	X	X
Mean (SD)		XX.X (XX.XX)	XX.X (XX.XX)	XX.X (XX.XX)	XX.X (XX.XX)	XX.X (XX.XX)	XX.X (XX.XX)	XX.X (XX.XX)	XX.X (XX.XX)	XX.X (XX.XX)	XX.X (XX.XX)	XX.X (XX.XX)	XX.X (XX.XX)	XX.X (XX.XX)	XX.X (XX.XX)
Median		XX.X	XX.X	XX.X	XX.X	XX.X	XX.X	XX.X	XX.X	XX.X	XX.X	XX.X	XX.X	XX.X	XX.X
Q1, Q3		XX.X, XX.X	XX.X, XX.X	XX.X, XX.X	XX.X, XX.X	XX.X, XX.X	XX.X, XX.X	XX.X, XX.X	XX.X, XX.X	XX.X, XX.X	XX.X, XX.X	XX.X, XX.X	XX.X, XX.X	XX.X, XX.X	XX.X, XX.X
Min, Max		XX, XX	XX, XX	XX, XX	XX, XX	XX, XX	XX, XX	XX, XX	XX, XX	XX, XX	XX, XX	XX, XX	XX, XX	XX, XX	XX, XX
Duration of Exposure (Days)	n	X	X	X	X	X	X	X	X	X	X	X	X	X	X
Mean (SD)		XX.X (XX.XX)	XX.X (XX.XX)	XX.X (XX.XX)	XX.X (XX.XX)	XX.X (XX.XX)	XX.X (XX.XX)	XX.X (XX.XX)	XX.X (XX.XX)	XX.X (XX.XX)	XX.X (XX.XX)	XX.X (XX.XX)	XX.X (XX.XX)	XX.X (XX.XX)	XX.X (XX.XX)
Median		XX.X	XX.X	XX.X	XX.X	XX.X	XX.X	XX.X	XX.X	XX.X	XX.X	XX.X	XX.X	XX.X	XX.X
Q1, Q3		XX.X, XX.X	XX.X, XX.X	XX.X, XX.X	XX.X, XX.X	XX.X, XX.X	XX.X, XX.X	XX.X, XX.X	XX.X, XX.X	XX.X, XX.X	XX.X, XX.X	XX.X, XX.X	XX.X, XX.X	XX.X, XX.X	XX.X, XX.X
Min, Max		XX, XX	XX, XX	XX, XX	XX, XX	XX, XX	XX, XX	XX, XX	XX, XX	XX, XX	XX, XX	XX, XX	XX, XX	XX, XX	XX, XX
Nivolumab															
Number of Doses Received	n	X	X	X	X	X	X	X	X	X	X	X	X	X	X
Mean (SD)		XX.X (XX.XX)	XX.X (XX.XX)	XX.X (XX.XX)	XX.X (XX.XX)	XX.X (XX.XX)	XX.X (XX.XX)	XX.X (XX.XX)	XX.X (XX.XX)	XX.X (XX.XX)	XX.X (XX.XX)	XX.X (XX.XX)	XX.X (XX.XX)	XX.X (XX.XX)	XX.X (XX.XX)
Median		XX.X	XX.X	XX.X	XX.X	XX.X	XX.X	XX.X	XX.X	XX.X	XX.X	XX.X	XX.X	XX.X	XX.X
Q1, Q3		XX.X, XX.X	XX.X, XX.X	XX.X, XX.X	XX.X, XX.X	XX.X, XX.X	XX.X, XX.X	XX.X, XX.X	XX.X, XX.X	XX.X, XX.X	XX.X, XX.X	XX.X, XX.X	XX.X, XX.X	XX.X, XX.X	XX.X, XX.X
Min, Max		XX, XX	XX, XX	XX, XX	XX, XX	XX, XX	XX, XX	XX, XX	XX, XX	XX, XX	XX, XX	XX, XX	XX, XX	XX, XX	XX, XX
Total Dose Received (mg)	n	X	X	X	X	X	X	X	X	X	X	X	X	X	X
Mean (SD)		XX.X (XX.XX)	XX.X (XX.XX)	XX.X (XX.XX)	XX.X (XX.XX)	XX.X (XX.XX)	XX.X (XX.XX)	XX.X (XX.XX)	XX.X (XX.XX)	XX.X (XX.XX)	XX.X (XX.XX)	XX.X (XX.XX)	XX.X (XX.XX)	XX.X (XX.XX)	XX.X (XX.XX)
Median		XX.X	XX.X	XX.X	XX.X	XX.X	XX.X	XX.X	XX.X	XX.X	XX.X	XX.X	XX.X	XX.X	XX.X
Q1, Q3		XX.X, XX.X	XX.X, XX.X	XX.X, XX.X	XX.X, XX.X	XX.X, XX.X	XX.X, XX.X	XX.X, XX.X	XX.X, XX.X	XX.X, XX.X	XX.X, XX.X	XX.X, XX.X	XX.X, XX.X	XX.X, XX.X	XX.X, XX.X
Min, Max		XX, XX	XX, XX	XX, XX	XX, XX	XX, XX	XX, XX	XX, XX	XX, XX	XX, XX	XX, XX	XX, XX	XX, XX	XX, XX	XX, XX
Number of Days of Exposure	n	X	X	X	X	X	X	X	X	X	X	X	X	X	X
Mean (SD)		XX.X (XX.XX)	XX.X (XX.XX)	XX.X (XX.XX)	XX.X (XX.XX)	XX.X (XX.XX)	XX.X (XX.XX)	XX.X (XX.XX)	XX.X (XX.XX)	XX.X (XX.XX)	XX.X (XX.XX)	XX.X (XX.XX)	XX.X (XX.XX)	XX.X (XX.XX)	XX.X (XX.XX)
Median		XX.X	XX.X	XX.X	XX.X	XX.X	XX.X	XX.X	XX.X	XX.X	XX.X	XX.X	XX.X	XX.X	XX.X
Q1, Q3		XX.X, XX.X	XX.X, XX.X	XX.X, XX.X	XX.X, XX.X	XX.X, XX.X	XX.X, XX.X	XX.X, XX.X	XX.X, XX.X	XX.X, XX.X	XX.X, XX.X	XX.X, XX.X	XX.X, XX.X	XX.X, XX.X	XX.X, XX.X
Min, Max		XX, XX	XX, XX	XX, XX	XX, XX	XX, XX	XX, XX	XX, XX	XX, XX	XX, XX	XX, XX	XX, XX	XX, XX	XX, XX	XX, XX

Note: Number of Days Exposure = Date of Last Dose of Study drug - Date of First Dose of Study drug + 1.
Note: No subjects were recruited into Cohort D and so this cohort is not displayed.

Source: Listing 16.2.5.1 and 16.2.5.2

Table 14.2.1
Response (RECIST v1.1)
Response Evaluable Analysis Set

	Cohort F Rare Tumors (N = XX)								Cohort H Ovarian (N = XX)	
					Sarcoma (N= XX)				Cohort G Post-CPI (N = XX)	Cohort H Ovarian (N = XX)
	Cohort A EC CPI-Naive (N = XX)	Cohort C Cervical (N = XX)	Cohort E TMB-H/MSS (N = XX)	Uveal (N = XX)	De-Diff LPS (N = XX)	UPS (N = XX)	GCT (N = XX)			
Confirmed CR	X (XX.X)	X (XX.X)	X (XX.X)	X (XX.X)	X (XX.X)	X (XX.X)	X (XX.X)	X (XX.X)	X (XX.X)	X (XX.X)
Unconfirmed CR	X (XX.X)	X (XX.X)	X (XX.X)	X (XX.X)	X (XX.X)	X (XX.X)	X (XX.X)	X (XX.X)	X (XX.X)	X (XX.X)
Confirmed PR	X (XX.X)	X (XX.X)	X (XX.X)	X (XX.X)	X (XX.X)	X (XX.X)	X (XX.X)	X (XX.X)	X (XX.X)	X (XX.X)
Unconfirmed PR	X (XX.X)	X (XX.X)	X (XX.X)	X (XX.X)	X (XX.X)	X (XX.X)	X (XX.X)	X (XX.X)	X (XX.X)	X (XX.X)
1 SD [1]	X (XX.X)	X (XX.X)	X (XX.X)	X (XX.X)	X (XX.X)	X (XX.X)	X (XX.X)	X (XX.X)	X (XX.X)	X (XX.X)
2 SD [1]	X (XX.X)	X (XX.X)	X (XX.X)	X (XX.X)	X (XX.X)	X (XX.X)	X (XX.X)	X (XX.X)	X (XX.X)	X (XX.X)
PD	X (XX.X)	X (XX.X)	X (XX.X)	X (XX.X)	X (XX.X)	X (XX.X)	X (XX.X)	X (XX.X)	X (XX.X)	X (XX.X)
NE	X (XX.X)	X (XX.X)	X (XX.X)	X (XX.X)	X (XX.X)	X (XX.X)	X (XX.X)	X (XX.X)	X (XX.X)	X (XX.X)
Objective Response Rate	X (XX.X)	X (XX.X)	X (XX.X)	X (XX.X)	X (XX.X)	X (XX.X)	X (XX.X)	X (XX.X)	X (XX.X)	X (XX.X)
95% CI	XX.X, XX.X	XX.X, XX.X	XX.X, XX.X	XX.X, XX.X	XX.X, XX.X	XX.X, XX.X	XX.X, XX.X	XX.X, XX.X	XX.X, XX.X	XX.X, XX.X
Disease Control Rate	X (XX.X)	X (XX.X)	X (XX.X)	X (XX.X)	X (XX.X)	X (XX.X)	X (XX.X)	X (XX.X)	X (XX.X)	X (XX.X)
95% CI	XX.X, XX.X	XX.X, XX.X	XX.X, XX.X	XX.X, XX.X	XX.X, XX.X	XX.X, XX.X	XX.X, XX.X	XX.X, XX.X	XX.X, XX.X	XX.X, XX.X

Response as per RECIST v1.1: CR = Complete Response, PR = Partial Response, SD = Stable Disease, PD = Progressive Disease.

De-Diff LPS = Dedifferentiated Liposarcoma, UPS = Undifferentiated pleomorphic sarcoma, GCT = Germ Cell Tumors.

[1] 1 SD includes Stable Disease following one scan. 2 SD includes Stable Disease following 2 or more scans.

Note: Objective Response Rate is calculated as the number of subjects with a confirmed complete response or partial response divided by the number of subjects in the analysis set.

Note: Disease Control Rate is calculated as the number of subjects with a confirmed complete response, partial response or stable disease divided by the number of subjects in the analysis set.

Note: No subjects were recruited into Cohort D and so this cohort is not displayed.

Note: No subjects in Cohort B are in the Response-Evaluable Analysis Set and so this cohort is not displayed here.

Source: Listing 16.2.6.4.1

This table shell will be used for

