6.3. Response Evaluation Criteria in Solid Tumors

Assessment of response and progression status in all subjects will be evaluated using the definitions from RECIST v1.1 for clinical decision-making and assessment of endpoints. Evaluation for target, non-target, and new lesions based on RECIST v1.1 are to be considered.

For a best overall response of CR or PR, confirmation of the response is required at a subsequent timepoint at least 4 weeks after the initial observation. Confirmed CR or PR will be claimed only if the criteria for each are met at that subsequent timepoint as outlined in [Appendix 7](#).

Table 2 Evaluation of Best Overall Response When Confirmation of CR and PR Required

Overall Response		Best Overall Response at that Time Point
First Time Point	Second Time Point	
CR	CR	CR
CR	PR	SD, PD, or PR ^a
CR	SD	SD provided minimum criteria for SD duration met ^b , otherwise, PD
CR	PD	SD provided minimum criteria for SD duration met ^b , otherwise, PD
CR	NE	SD provided minimum criteria for SD duration met ^b , otherwise, PD
PR	CR	PR
PR	PR	PR
PR	SD	SD
PR	PD	SD provided minimum criteria for SD duration met ^b , otherwise, PD
PR	NE	SD provided minimum criteria for SD duration met ^b , otherwise, PD

Abbreviations: CR = complete response; NE = not evaluable; PD = progressive disease; PR = partial response; SD = stable disease.

^a If a CR is truly met at the first timepoint, then any disease seen at a subsequent timepoint, even disease meeting PR criteria relative to baseline, makes the disease PD at that point (since disease must have reappeared after CR). Best response would depend on whether minimum duration for SD was met. However, CR may be claimed when subsequent scans suggest small lesions were likely still present and in fact the subject had PR, not CR at the first timepoint. Under these circumstances, the original CR should be changed to PR and the best response is PR.

^b Minimum required duration of SD is 6 weeks.

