9.3.1. Efficacy Analyses

Efficacy analyses will be performed separately for each cohort. RECIST 1.1 criteria will be used for the primary endpoint evaluation ([Eisenhauer et al., 2009](#)), and iRECIST will be used for the exploratory endpoint response evaluation ([Seymour et al., 2017](#)). The iRECIST endpoints are analyzed using the same statistical methodology and the results will be presented in the same ways for the corresponding RECIST 1.1 endpoints.

The primary efficacy endpoint is the ORR defined as the proportion of subjects who achieve confirmed CR or PR per RECIST v1.1. The best overall response is the best response recorded from the start of the treatment until PD. The smallest measurements recorded since the treatment started will be used as the reference for PD. Subjects with CR or PR are considered to have obtained objective response. Subjects with not-evaluable response (NE) are counted as non-responders. Exact 95% CI will be constructed for the ORR for each cohort.

Subjects with CR, PR or SD are considered to have achieved disease control. Disease control rate is defined as the proportion of subjects who have achieved CR, PR, and SD. Duration of response only applies to subjects whose best overall response is CR or PR and is defined as the number of days from the first documentation of objective tumor response to the date of first PD or death due to underlying cancer.

Duration of stable disease is measured from the start of the treatment (the first treatment date for non-randomized studies, the randomization date for randomized studies) until the date when the criteria for overall disease progression are first met.

Duration of response is the time from first evaluation showing CR or PR (response confirmation required at subsequent tumor assessment no earlier than 4 weeks after first evaluation showing CR or PR) to the time of the first subsequent evaluation showing PD or death. Only subjects who experience a confirmed CR or PR will be analyzed for DoR. Subjects who do not experience PD or death will be censored per the censoring rules in the statistical analysis plan.

Progression-free survival is defined as the number of days from Day 1 in Cycle 1 to the first documented progression or death due to any cause. Only deaths that occurred within 30 days of the last progression assessed.

Overall survival is defined as the time from the first dose of study drug to death due to any cause.

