7.2. Secondary Endpoints

- Count and % of subjects who experience at least 1 adverse event (AE) and abnormal safety laboratory parameters
- Adverse events of special interest [(AESIs) infusion reactions, immune-related adverse events)]
- Relationship of PK and safety
- Disease control rate (DCR; is the proportion of subjects whose Best Overall Response is CR, PR, or SD)
- Duration of response (DoR)
- Duration of stable disease
- PK levels of etigilimab in combination with nivolumab
- Anti-drug antibodies (ADA) to etigilimab; Impact of developed etigilimab ADAs on PK levels of etigilimab

Note PK and ADA endpoints will not be evaluated as part of the analyses specified within this SAP.

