For either CR or PR to be ‘confirmed’ the same overall response needs to be achieved at the subsequent visit, which should be at least 4 weeks later. The best overall response (BOR) is then the best response achieved in order of CR, PR, SD, PD, NE, where a subject cannot be defined as having BOR of CR, PR or SD if they have previously experienced PD.

Response is recorded for each participant at each tumor response visit using the criteria outlined above. The response recorded in the database will be used to evaluate the objective response rate and all other endpoints related to the response based on RECIST v1.1 guidelines.

Objective Response Rate (ORR) is then defined as the proportion of subjects who achieve a best overall response of Confirmed CR or Confirmed PR. Subjects with not-evaluable response (NE) are counted as non-responders.

The number and percentage of subjects who have achieved objective response will be summarised, by cohort, including sub-cohort, along with the 95% Clopper-Pearson CI.

Additionally the number and percentage of subjects with CR and PR (confirmed and unconfirmed), SD, PD and NE will be summarised by cohort, including sub-cohort.

A swimmer plot, displaying the response for each subject over their time in the study, will be presented for all subjects as well as for gynaecological cohorts (Cohort A, E and H) and rare tumor sub-cohorts (Cohort F) with a line per subject and each response/important event highlighted on the line as appropriate.

A waterfall plot will also display the percentage reduction in overall sum of diameters over the time in study for each subject. This will again be presented for all subjects and for gynaecological cohorts

(Cohort A, E and H) and rare tumor sub-cohorts (Cohort F). Additionally a spider plot will be produced for each set of cohorts, which will display the percentage change from baseline in sum of the longest diameter over time, where the lines will be displayed by best overall response.

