10.8.2. Secondary Endpoints

10.8.2.1. Disease Control Rate

Disease control rate (DCR) is defined as the proportion of subjects who have achieved CR, PR, and SD. The number and percentage of subjects who have achieved disease control will be summarised, by cohort, including sub-cohort, along with the 95% Clopper-Pearson CI.

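### The SAP defines disease control rate inconsistently: the Table 14.2.1 note leaves out unconfirmed CR/PR, the SAP text does not, and protocol Table 2 is not carried into the best-overall-response rule

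*SAP*

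**What the plan says.** Four places bear on how DCR is counted.

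- **SAP Section 14, notes to Table 14.2.1.** The DCR note is "Disease Control Rate is calculated as the number of subjects with a confirmed complete response, partial response or stable disease divided by" the number in the analysis set. The ORR note just above it has the same construction: "Objective Response Rate is calculated as the number of subjects with a confirmed complete response or partial response divided by" the same denominator. The shell has separate rows for confirmed CR, unconfirmed CR, confirmed PR, unconfirmed PR, 1 SD, 2 SD, PD and NE. The same shell serves Table 14.2.4 (iRECIST).
- **SAP text.** Section 7.2 says DCR "is the proportion of subjects whose Best Overall Response is CR, PR, or SD". Section 10.8.2.1 says "Disease control rate (DCR) is defined as the proportion of subjects who have achieved CR, PR, and SD". Section 10.8.1.1 ranks best overall response as CR, PR, SD, PD, NE and adds: "Additionally the number and percentage of subjects with CR and PR (confirmed and unconfirmed), SD, PD and NE will be summarised". It gives no rule for reclassifying a response that is not confirmed.
- **Protocol 9.3.1.** "Subjects with CR, PR or SD are considered to have achieved disease control". SAP 10.8.2.1 restates this definition.
- **Protocol 6.3, Table 2.** A best overall response of CR or PR needs confirmation at least 4 weeks later. PR then SD is SD. PR then PD or NE, and CR then SD, PD or NE, are "SD provided minimum criteria for SD duration met", and otherwise PD. CR then PR is SD, PD or PR. PR then CR is PR. The minimum SD duration is 6 weeks.

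SAP section 11, which lists changes from the protocol analysis, has no entry on DCR or best overall response.

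**The concern.** A programmer working from the shell would compute DCR as confirmed CR plus confirmed PR plus SD. A subject with PR at week 8 and PD at week 16 would sit in the unconfirmed PR row and outside the DCR numerator. A subject with SD at week 8 and PD at week 16 would be inside it. The deeper response would then rank below the shallower one, which neither the protocol nor the SAP text intends.

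At stake are the value and confidence interval of a secondary efficacy endpoint in each cohort, and the SD count in the best-response distribution. With small cohorts, one subject moves the rate visibly. If the conflict is left open, the choice of numerator could also be made after the unconfirmed counts are known.

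**Working it through.** The documents give no DCR figure, so there is nothing to reproduce. The check sets the rules side by side and then sizes the difference.

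**Step 1. What the note covers.** SAP 10.8.1.1 defines ORR by confirmed CR or confirmed PR, so in the ORR note the word *confirmed* must govern both. The DCR note has the same construction, so its natural reading is confirmed CR, confirmed PR, or SD.

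**Step 2. Where unconfirmed responders go.** They have their own rows. The table's source, Listing 16.2.6.4.1, carries one best overall response per subject, which suggests that the rows are exclusive, although the SAP does not say so.

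**Step 3. Sequences compared** (assuming that no later scan confirms the response).

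| First, then second assessment | Protocol Table 2 | DCR from Table 2 | DCR from SAP 7.2 and 10.8.2.1 with the SAP ranking | DCR from the note, rows exclusive |
|---|---|---|---|---|
| PR, SD | SD | counts | counts | does not count |
| PR, PD or NE | SD if 6 weeks met, otherwise PD | counts if 6 weeks met | counts | does not count |
| CR, then SD, PD or NE | SD if 6 weeks met, otherwise PD | counts if 6 weeks met | counts | does not count |
| CR, PR | SD, PD or PR | depends on the case | counts | does not count |
| PR, CR | PR | counts | counts | does not count if the SAP's same-response rule for confirmation is taken literally |

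**Step 4. Is the 6-week condition usually met?** Protocol 6.1 and 8.2 schedule scans every 8 weeks with a window of 1 week. The earliest scheduled scan is week 8 − 1 = 7, or 7 × 7 = 49 days. The minimum is 6 × 7 = 42 days. A response first seen at a scheduled scan therefore meets it. Only an unscheduled scan before week 6 could lead to PD by this route.

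**Step 5. Size.** Let N be the number in the cohort column and u the number of unconfirmed responders whom Table 2 classes as SD or PR. Then DCR(Table 2) − DCR(note) = u/N.

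- u = 1: 1/10 = 10.0 points; 1/20 = 5.0 points; 1/29 = 3.4 points.

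Illustrations with assumed counts and exact Clopper-Pearson 95% intervals:

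| N | Confirmed + SD | u | DCR by the note | DCR by Table 2 |
|---|---|---|---|---|
| 10 | 1 + 3 | 1 | 4/10 = 40.0% (12.2–73.8) | 5/10 = 50.0% (18.7–81.3) |
| 10 | 1 + 3 | 2 | 4/10 = 40.0% (12.2–73.8) | 6/10 = 60.0% (26.2–87.8) |
| 20 | 2 + 6 | 1 | 8/20 = 40.0% (19.1–63.9) | 9/20 = 45.0% (23.1–68.5) |
| 29 | 4 + 9 | 1 | 13/29 = 44.8% (26.4–64.3) | 14/29 = 48.3% (29.4–67.5) |

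If u = 0 the two rules agree.

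**The case against.** The best defence is that the SAP's defining text is sound. Sections 7.2 and 10.8.2.1 match the protocol and do not ask for confirmation. On the SAP's own ranking, an unconfirmed PR counts as disease control. Section 4 promises that deviations from the protocol will be listed in section 11, and none is listed here, so the protocol's rule was arguably meant to stand. The note is also loosely worded: *confirmed* cannot govern the whole list, because protocol Appendix 7 does not require confirmation of SD. Finally, DCR is descriptive, SAP 10.1.3 plans no hypothesis test, and the unconfirmed counts are printed in the same table.

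Much of this stands. A reader might infer that the SAP scores every unconfirmed responder as having no disease control, and that the protocol makes every such subject SD. The documents support neither in full. The first rests on one table note, on rows whose exclusivity is not stated, and against two body sections that say otherwise. The second overlooks that Table 2 can also give PD or PR.

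The defence does not remove the conflict. SAP 10.1.2 sends the reader to Section 14 for the specific content of each table, so the note is what would be programmed. Printing the unconfirmed counts lets a reader add them back only if the rows are exclusive. The printed rate and interval would still be those of the note, and any subject whom Table 2 makes PD could not be told apart.

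**Conclusion.** The point holds as an internal inconsistency in the SAP together with a missing derivation step. On its natural reading the Table 14.2.1 note gives a different DCR numerator from SAP 7.2, SAP 10.8.2.1 and protocol 9.3.1, and SAP 10.8.1.1 does not say how an unconfirmed response enters best overall response, although protocol Table 2 does.

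If the note is followed, DCR is lower by 1/N for each unconfirmed responder whom Table 2 classes as SD or PR. This rests on reading *confirmed* as covering both CR and PR and on treating the rows as exclusive. The number of affected subjects is not given, so the actual shift may be zero. With 1 or 2 such subjects assumed, it is 10 to 20 points at N=10 and 3.4 to 6.9 points at N=29 (2/29 = 6.9).

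The DCR note does not touch ORR as defined in its own note, nor the Simon stopping and success rules, which concern objective response. This should be corrected, but it concerns a secondary descriptive endpoint and does not threaten the primary result.

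**What to change.** 1. In SAP 10.8.1.1, state that RECIST v1.1 best overall response follows protocol Table 2, including the 6-week minimum. This also settles PR then CR as PR, which the SAP's same-response wording leaves open.
2. In SAP 10.8.2.1, define DCR as a best overall response of CR, PR or SD under that rule, and reword the Table 14.2.1 note to match.
3. Keep the unconfirmed CR and PR counts as descriptive rows, with a note that each such subject is also counted in the Table 2 category (SD, PR or PD). They should not simply be made sub-rows of SD, because some belong to PR or PD.
4. For Table 14.2.4, either drop the DCR row, since neither document lists DCR as an iRECIST endpoint, or derive it from the iRECIST best-overall-response rules. Table 2 is a RECIST v1.1 rule and should not be carried over.

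The cost is SAP and shell wording plus one derivation step, with no new data. It should be settled before the response tables are produced. If they already exist, the rule used belongs in the clinical study report, where SAP section 4 places departures from the SAP.
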